5.4 Participant Withdrawal or Termination

5.4.1 Reasons for Withdrawal or Termination

Participants may withdraw from the study at any time by contacting the study team via email or in writing. Participants who prematurely discontinue study agent treatment will still be encouraged to return for the 42-day (6 week) follow-up study visit.

Participants may also be withdrawn from the study at any time per the discretion of the principal investigator (PI).

The PI will withdraw legally authorized representative (LAR)-consented participants if they display significant distress, are uncooperative, or if the LAR-consented participant indicates in any way that he or she does not wish to proceed with the LP or other procedures, per the PI's clinical judgement. The LAR should be present during trial procedures to act as an advocate and to request withdrawal if needed, unless this is impossible due to hospital/health system regulations during the covid19 or other exigent circumstances.

5.4.2 Handling of Participant Withdrawals or Terminations

A recent phase I trial did not identify any specific adverse events or safety concerns with CN-105 (Guptill J et al, 2017). Nonetheless, if at any time during the dosing period, participant safety is considered at risk due to study agent-related adverse events per the judgement of the external Data Safety Monitoring Board (or DSMB+) and the PI, then the study agent will be immediately discontinued. Although the DSMB+ is only scheduled to convene and review reports (including grade II or higher AE, and SAE information) at the completion of each 67 patient cohort, the PI may also request that the independent statistician prepare additional interim analyses and provide these to the DSMB+ at any time. For example, this may be useful and/or appropriate if there is a severe SAE (such as a patient death) and the PI wishes to have the DSMB+ review grade II or higher AE rates and data up to an including this severe SAE, and make interim recommendations to the study team.

Since CN-105 modulates the inflammatory response, it could theoretically impair the response to infection. Thus, in an abundance of caution, the study agent will be discontinued in any patient who develops any intracerebral or systemic infection.

If a participant has clinically significant laboratory and/or electrocardiographic abnormalities that are considered to be related to the study agent in the judgement of the Principal Investigator or the DSMB, study agent treatment discontinuation will be evaluated.

Primary study analyses will be conducted using intention to treat analysis (i.e. with patients included in the groups to which they were randomized even if they did not correctly receive all doses to which they were randomized); secondary analysis may be conducted using as treated analyses (i.e. with patients grouped by the drug doses actually received).

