7.4 Trial Schedule

7.4.1 Initial Consent and Visit

The following procedures and assessments will be conducted at the time of initial study consent or between the Initial study consent and the day of surgery:

Informed consent

Enrollment

Demographics (age, sex, and race)

Medical history

Neurocognitive testing will be done either in-person or remotely via teleconference (may include WTAR; HVLT-R; BVMT-R; WAIS-III —Digit Span, Digit Symbol Coding subtests, TrailTMT, Parts A & B, COWAT and Grooved Pegboard; MoCA) as well as the STOPBang assessment, VAS pain assessment, Falls assessments, Timed Up and Go Test, and Romberg Test

DASI

Psychological measures (including CES-D, STAI, SCL-90, SF-36)

Record concomitant medications administered per standard of care

Delirium Screening with the 3D-CAM instrument

Collect CSF sample/ LP prior to surgery (i.e. between the time of consent and the time of scheduled anesthesia/surgery start, which means it could be done at the initial visit or anytime between the time of consent at the initial visit and the time of scheduled anesthesia/surgery start on the day of surgery)

Collect research blood sample prior to surgery (i.e. between the time of consent and the time of scheduled anesthesia/surgery start, which means it could be done at the initial visit or anytime between the time of consent at the initial visit and the time of scheduled anesthesia/surgery start on the day of surgery)

LP vital signs will be collected and recorded by the study team before and after the LP if performed on outpatient basis (between

the time of consent and surgery day).

If the LP is performed while the patient is an inpatient (i.e. on the day of surgery), the study team will not collect and record vital signs, as these will already be obtained by the patient's clinical care team and recorded in the hospital electronic medical record for the patient, per standard of care.

-Randomization assignments will be made within 1 week prior to the patient's scheduled surgery.

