7.4.2 Day 0 (Day of Surgery)

The following procedures and assessments will be conducted at this visit:

Collect CSF sample/ LP prior to surgery (if not done at the time of the Initial Consent and Visit)

Concomitant medications administered per standard of care.

Collect blood sample (if not done at the time of the Initial Consent and Visit)

Laboratory assessments

Study drug or placebo administration (within one hour prior to scheduled or actual surgery start time, and subsequent drug doses will be given every 6 hours thereafter until 3 days after surgery or hospital discharge, whichever comes first, up to a maximum of 13 doses) by the patient's clinical care team. Each case start time will be defined by the study team as either the start of the surgery/procedure or the start of anesthesia. If the case gets delayed by more than 6 hr and we've already given the first dose, we will give an additional dose prior to surgery, but under no conditions will the patient be given more than 13 doses total of CN-105.

EEG (within 2 hours before surgery as well as during and just aftersurgery). In the event that sufficient personnel or equipment are unavailable, or in the event that two MARBLE patients are having surgery at the same time, or in the event that there is insufficient time to place the EEG sensor on that patient's head before the start of surgery, the study team may not record EEG from all patients or at all points before, during, and just after surgery/anesthesia. Auditory tones will be played and auditory event-related potentials will be recorded if the pre-op and surgical workflow allows and if study personnel are available.

Vital signs (including heart rate) will be obtained and entered into the anesthetic record during the surgery by the clinical care team as per GCP, standard of care, and the American Society of Anesthesiology guidelines .

Continuous heart rate monitoring will be obtained for up to 15 minutes prior to surgery and during the surgery, to assess heart rate variability (R-R interval) as an index of vagal nerve function.

Grade II or higher AEs (and all SAEs) will be monitored and recorded from just after the first study drug or placebo administration until the end of the 6 week +/- 3 weeks postoperative study follow up visit.

Delirium Screening may be administered with 3D-CAM or CAM-ICU up to two times after surgery.

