8.3 Time Period and Frequency for Event Assessment and Follow-up

The investigator will record all reportable events starting from the time just after the first administration of study drug (or placebo) until the last trial-related procedure/visit. At each trial visit, the investigator or study team will inquire about the occurrence of grade II or higher AE and any SAEs since the last visit. Events will be followed for outcome information until resolution or stabilization. Adverse events of grade II or higher for participants who discontinue trial participation will be collected/reported through at least the time of discontinuation.

When additional relevant information (final diagnosis, outcome, results of specific investigations, etc.) becomes available, the investigator will submit this additional information to the DSMB at the time of the next DSMB report (or earlier, if deemed appropriate by the PI).

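### The primary adverse-event population is inconsistent: analysis is by intention to treat, events are recorded only after the first dose, and the endpoint text refers to patients treated

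*Combined protocol and SAP*

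**What the plan says.** **Analysis principle.** Section 5.4.2: "Primary study analyses will be conducted using intention to treat analysis". Patients stay in their randomised group "even if they did not correctly receive all doses to which they were randomized". The only alternative is optional: "secondary analysis may be conducted using as treated analyses", with patients grouped by what they actually received. A patient with no dose at all is not mentioned.

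**AE window.** Section 7.4.2: "Grade II or higher AEs (and all SAEs) will be monitored and recorded from just after the first study drug or placebo administration". Section 8.3 sets the same start, with events recorded "starting from the time just after the first administration of study drug (or placebo) until the last trial-related procedure/visit". Section 8.4 agrees.

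**Randomisation and cohort closure.** Section 7.4.1: "Randomization assignments will be made within 1 week prior" to the scheduled operation. Section 10.3.1 gives the same limit, and Section 6.2 allows the week or the day of surgery. The first dose comes no more than an hour ahead of the planned or real start (Section 6.2). Cohorts two and three close on 67 patients randomised, not 67 dosed (Sections 4.1, 8.5 and 10.1.2).

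**Endpoint wording.** The Protocol Summary compares participants who receive CN-105 with those who receive placebo. Section 4.2.1 compares each dose cohort with those who receive placebo. Section 10.1.2 refers to CN-105-treated and placebo-treated patients. No safety analysis set is defined in Section 5.4 or Section 10.

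**The concern.** A randomised patient can go undosed, for example if the operation is cancelled after assignment. That patient has no AE window. Under a literal intention-to-treat rule the patient adds one to the denominator and cannot add to the numerator. Under the wording of the endpoint and safety sections the patient would not be in the comparison at all. The plan does not choose between these.

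The direction matters because the primary question is whether the drug raises the AE rate. Including patients who cannot have a recorded event is usually accepted as conservative for efficacy. For harm it works the other way, by drawing the absolute difference toward zero. There is also a procedural risk: with two readings available and no rule, the denominator could be chosen after the treatment codes are known. The DSMB reports, which compare AE rates by arm after each cohort, have the same undefined denominator.

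**Working it through.** **Inputs**
- Placebo AE rate 5% (Section 10.2); detectable difference 14.8 points (Sections 10.1.2 and 10.2); hence a CN-105 rate of 5 + 14.8 = 19.8%.
- Group sizes 117 and 39 (Section 10.1.2). Randomised totals 3 x 50 = 150 and 3 x 17 = 51 (Table 1), ignoring the two extra patients in cohort one, whose arms are not stated.
- Two-sided test, unpooled variance, alpha 0.05.
- Undosed fraction u: not in the documents. Assumed 2%, 5% and 10%, equal in both arms.

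**Step 1: reproduce the plan's figure.** SE = sqrt(0.05 x 0.95/39 + 0.198 x 0.802/117) = 0.0507. Then z = 0.148/0.0507 = 2.92, and power = Phi(2.92 - 1.96) = 83.1%. Exact binomial enumeration of the same test gives 80.1%. Both agree with the stated power above 80%.

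**Step 2: dilution.** If undosed patients are scored event-free, each arm's expected rate is multiplied by (1-u):

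difference = 0.198(1-u) - 0.05(1-u) = 0.148(1-u)

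risk ratio = 0.198(1-u) / [0.05(1-u)] = 3.96 for every u

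**Step 3: power (normal approximation), all randomised versus dosed only.** The dosed-only analysis keeps the rates at 5% and 19.8% and multiplies the group sizes by (1-u).

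| u (assumed) | Expected difference, all randomised | Power at 117/39: all randomised / dosed only | Power at 150/51: all randomised / dosed only |
|---|---|---|---|
| 2% | 14.5 points | 82.2% / 82.3% | 90.7% / 90.7% |
| 5% | 14.1 points | 80.8% / 81.1% | 89.6% / 89.9% |
| 10% | 13.3 points | 78.4% / 79.0% | 87.8% / 88.2% |

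Keeping undosed patients in the denominator costs at most 0.6 points of power here. Section 10.1.2 gives 5% each for moderate and severe events, so a 10% placebo rate was also tried; the cost is then at most 0.9 points over the same u.

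**Step 4: scale against sampling error.** At u = 10% the shift is 14.8 - 13.3 = 1.5 points. The SE of the difference is 5.1 points at 117/39 and sqrt(0.05 x 0.95/51 + 0.198 x 0.802/150) = 4.5 points at 150/51. The shift is therefore about 0.3 of one standard error.

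**Step 5: unequal fractions.** If 10% were undosed on CN-105 only, the difference would be 19.8 x 0.9 - 5 = 12.8 points. If 10% were undosed on placebo only, it would be 19.8 - 5 x 0.9 = 15.3 points. Imbalance can move the estimate either way.

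**The case against.** A reader might infer that the plan scores undosed patients as event-free and so builds a bias into its primary result. The documents do not support that. The intention-to-treat sentence is explained by reference to incomplete or incorrect dosing, and zero-dose patients are not named. Someone with no AE window could equally be treated as having no AE data. The endpoint and safety text points toward treated patients. It does not settle the matter, because the same words label the randomised arms elsewhere: Section 4.1 and Table 1 say 50 receive drug and 17 placebo out of 67 randomised.

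The size is also open to challenge. No undosed fraction is given. Randomisation may fall on the day of surgery, and not every consented patient is randomised, so undosed cases may be few. The shift is small against sampling error, the risk ratio does not move, and the pull toward zero holds only in expectation with equal undosed fractions. With about 51 placebo patients, chance imbalance could push the other way.

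These points stand, and they limit the claim. They do not remove it. The plan has two readings of its primary denominator. The as-treated analysis does not close the gap, because it is optional and has no rule for a patient with no dose.

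A reader might also fear for the 10% limb of the stopping guideline in Section 5.4.3. With 50 drug patients per cohort, five events are needed to reach 10%, and five are still needed with 41 dosed. A few undosed patients would not change that count.

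**Conclusion.** The concern holds as an inconsistency in the primary safety population. It does not hold as a demonstrated bias. Section 5.4.2 read literally includes patients who cannot have a recorded event, the endpoint and safety sections suggest otherwise, and no rule decides.

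If the literal reading were applied with undosed patients scored event-free, the expected absolute difference would fall by 0.3, 0.7 or 1.5 points at u of 2%, 5% or 10%. This rests on an assumed u, equal in both arms, and on the plan's own 5% and 14.8-point figures. Loss of power is not a reason to act. The reasons are the direction of the effect on a safety endpoint and the need to fix the denominator before the treatment codes are released. The change is worth making because it costs so little.

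**What to change.** In Sections 5.4.2 and 10.1.2:

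- Define the primary safety set as all randomised patients who received at least one dose of CN-105 or placebo, grouped as randomised. Use the same set for the DSMB reports.
- Make a version grouped by treatment actually received a required companion analysis, restricted to the same dosed patients.
- Report the number randomised but undosed, by arm.
- Keep full intention to treat for the efficacy endpoints and as an AE sensitivity analysis, stating there that undosed patients are counted as event-free.
- Align the wording of the Protocol Summary and Section 4.2.1 with this set.

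The cost is text only: the randomisation list and the dose records required by Section 6.3 already hold what is needed. The change should be made before the primary statistician receives the randomisation list. The downside is a slightly smaller denominator. Leaving out undosed patients should not select by arm, because Sections 10.3.1 and 10.3.2 keep study staff and clinicians blinded. Chance imbalance remains possible, which is why the counts by arm should be shown.

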5.4.3 Premature Termination or Suspension of Trial

At the end of each 67 patient dose cohort, grade II or higher AEs and any SAEs will be provided to

and reviewed by the DSMB+ and the PI, who will then consider whether the study can continue or whether it needs to be stopped

and/or whether other corrective action needs to take place. The external DSMB+ or the PI may also request additional interim analyses.

The study may be stopped if after any group of 67 patients the rate of grade III or higher SAEs (per CTCAE guidelines) in drug-treated patients is at least 10% and more than three times the rate of such events in the placebo-treated group. Considering the wide range of surgical procedures and patient comorbidities that could contribute to adverse events seen in this study, the DSMB+ should use both this quantitative cutoff and its clinical judgement in considering whether to stop the study. The study may be modified at any time by the sponsor, the FDA, or the external IRB as part of their duties to ensure that research subjects are protected.

6 STUDY AGENT

6.1 Study Agent and Control Description

6.1.1 *Acquisition*

CN-105 will be supplied by AegisCN and manufactured under contract by University of Iowa Pharmaceuticals, Iowa City IA. Study drug will be shipped directly from the manufacturer to the Duke pharmacy, whose investigational drug service will then dispense the drug at each participating study site (Duke Hospital, Duke Regional Hospital, Duke Raleigh Hospital).

6.1.2 *Formulation, Appearance, Packaging, and Labeling*

CN-105 will be supplied in amber glass vials containing 4 mL of a concentrated, 12.5-mg/mL, clear-to-slightly-yellow solution. The vials are stoppered and capped with over-seals. Cloudiness, change in color, and/or the presence of any particulate matter may indicate that the product has deteriorated; if any of these or other changes are noted, the affected vials will not be used, and the study team will communicate with AegisCN and the University of Iowa Pharmaceuticals as soon as possible.

Vials of CN-105 will have the following labeling information:

CN-105 12.5 mg/mL (50 mg/vial)

Store frozen at -70°C

Caution: New Drug—Limited by Federal (U.S.) Law to Investigational Use

Dosing labels will be attached to each dosing syringe/infusion bag. The individual participant syringe/infusion bag label will include both preprinted fields and handwritten fields as follows:

Protocol number

Personal identification number

Participant initials

Date

Time

Volume

6.1.3 *Product Storage and Stability*

If dosing solutions are prepared more than 1 hour before the planned start of the study drug infusion, the infusion bags containing the dosing solutions are to be refrigerated at 2 to 8°C in a secure and

locked refrigerator (and/or in a refrigerator in a secure and locked room). The drug can be refrigerated for up to 24 hours until approximately 60 minutes before the planned start of the infusion.

6.1.4 Preparation

Study drug will be diluted in normal saline by the Investigational Drug Service (IDS); placebo will be normal saline. The infusion will be administered using a 1.2-micron or smaller filter.

6.2 Dosage and Administration

We planned to enroll up to 250 patients total in this phase 2 study to obtain three successive dose groups of 67 patients each. In each group of 67 patients, 50 will receive a given dose of CN-105, and 17 will receive placebo. Due to a clerical error by the Investigational Drug Services that prepares our drug/placebo doses, 69 patients were randomized to the first patient cohort rather than 67. Because enrollment happens at consent, and not all patients that consent will be randomized, we will keep enrolling patients until we reach 67 consented and randomized patients in each cohort.

In each successive 67 patient group, participants will be randomized the week or day of surgery to receive either CN-105 (see [Table 1 for dose levels](#)) or placebo, within one hour before the scheduled or actual surgery start time and continuing every 6 hours until postoperative day 3 or hospital discharge (whichever occurs first), up to a maximum of 13 doses.

6.2.1 Route of Administration

Study drug or placebo will be administered intravenously over 5-10 min, up to maximum of 30 minutes.

6.2.2 Starting Dose and Escalation Schedule

Patients who receive CN-105 will receive one of three dose levels depending on their cohort: 0.1 mg/kg, 0.5 mg/kg, or 1 mg/kg, depending on whether they are in the first, second or third group of 67 patients, respectively. The 6 week +/- 3 week follow up visits for patients in the first two cohorts may be completed while the next cohort (higher dose level) is starting to be enrolled.

Table 1: Dose levels of CN-105

Cohort	Dose of CN-105	Patients receiving drug	Patients receiving placebo
Dose level 1	0.1 mg/kg	50	17
Dose level 2	0.5 mg/kg	50	17
Dose level 3	1 mg/kg	50	17

6.2.3 Dose Adjustments/Modifications/Delays

At the end of each 67-patient enrollment/ randomization group, grade II or higher AE rates and safety information will be provided to the DSMB. Upon evaluating this information, the DSMB plus will then consider whether the study should be stopped or whether other corrective action should take place. While grade II and/or higher AE and safety information from a given 67 patient randomized group is being analyzed and provided to the DSMB plus, and while the DSMB plus is

evaluating this data (as described above), the trial will continue with enrollment of the next 67 patient group (who will receive either placebo or the next higher dose of CN-105). Due to a clerical error by the Investigational Drug Services that prepares our drug/placebo doses, 69 patients were randomized to the first patient cohort rather than 67.

There is no data from either preclinical studies or our recent phase I study suggesting any dose-dependent toxicity or side effects from CN-105. Thus, there is no reason to halt the enrollment of a subsequent 67 patient group (which will include patients receiving a higher dose of CN-105) while the DSMB is awaiting and then analyzing data from the prior 67 patient group. Nonetheless, the DSMB plus will be empowered to make recommendations about whether the trial should be stopped or modified based on their evaluation of data in the prior 67 patient group(s).

6.2.4 Duration of Therapy

Study drug will be administered every 6 hours, with the first dose within one hour of planned or actual case start time, and subsequent drug doses will be given every 6 hours thereafter until postoperative day 3 or hospital discharge, whichever occurs first, up to a maximum of 13 doses. Each case start time will be defined by the study team as either the start of the surgery/procedure or the start of anesthesia (or the timed notes in the EMR for induction, intubation, or the start of anesthetic drug administration). If the case gets delayed by more than 6 hr and we've already given the first dose, we will give an additional dose prior to surgery, but under no conditions will the patient be given more than 13 doses total of CN-105

